4.0 SUBJECT SCREENING AND REGISTRATION PROCEDURES

Patient registration for this trial will be centrally managed by the Coordinating Center of The University of Michigan Rogel Cancer Center as described below:

A potential study subject who has been screened for the trial and who has signed the Informed Consent document will be initially documented by the participating site on the Screening and Enrollment Log provided by the Coordinating Center.

It is the responsibility of the local site investigator to determine patient eligibility prior to submitting patient registration request to the Coordinating Center. After patient eligibility has been determined, a copy of the completed Eligibility Worksheet together with all the pertinent de-identified source documents will be submitted by the requesting site to the Coordinating Center, by email to [contact].

The Multi-Site Coordinator, who acts as the registrar, will review the submitted documents and process the registration. Sites should inform the Multi-Site Coordinator of a potential registration by 5 p.m. on the day prior to registration. Same day registrations cannot be guaranteed.

An email will be sent by the registrar to the requesting site registrar to confirm patient registration and to provide the study identification number that has been assigned to the patient. In addition, a copy of the Eligibility Worksheet signed and dated by the registrar, will be sent back to the requesting site registrar.

Patients found to be ineligible for participation after being consented will be considered screen failures, and documented as such in the Screening and Enrollment Log. These patients will not have study identification number assigned to them, and will not receive study treatment.

5.0 TREATMENT PLAN

5.1 Treatment Dosage and Administration

Protocol treatment must start within 5 business days of enrollment to the study.

5.1.1 This study will be a non-randomized phase II trial. We will enroll 40 patients with R/M HNSCC. Patients will be treated with Carboplatin (AUC=5, IV, day 1) as well as Palbociclib (125 mg, daily, days 1-14). Cycle length will be 21 days. Patients will be monitored closely for toxicity and undergo imaging to evaluate efficacy once every 2 cycles. After 6 cycles of Carboplatin + Palbociclib, if patients continue to garner a response to therapy, they will be transitioned to maintenance single agent palbociclib at a dose of 125 mg daily, days 1-21, cycle length: 28 days

5.1.2 Carboplatin + Palbociclib Regimen

REGIMENT DESCRIPTION					
Agent	Premedication; Precautions	Dose	Route	Schedule	Cycle Length
Carboplatin	Premedication per discretion of prescribing physician	AUC=5	IV	Days 1, week 1	
Palbociclib	Capules -Swallow capsules whole. Do not cut, chew, or crush -Should be taken with food at approximately the same time each day Solution -Should be taken at approximately the same time each day. Does not need to be taken with food.	125 mg daily	Capsule or Solution	Days 1-14	3 weeks (21 days)

5.1.2.1 Carboplatin Administration

5.1.2.1.1 Carboplatin is an IV drug which will be administered as an outpatient

5.1.2.1.2 Premedications per discretion of prescribing physician

5.1.2.2 Palbociclib Administration

5.1.2.2.1 Palbociclib will be self-administered and may be taken by mouth or via feeding tube.

5.1.2.2.1.1 If patients can swallow pills, Palbociclib will be administered as a capsule formulation

5.1.2.2.1.1.1 Swallow palbociclib capsules whole. Do not cut, chew, or crush capsules

5.1.2.2.1.1.2 Palbociclib capsules should be taken with food at approximately the same time each day

5.1.2.2.1.2 If patients are unable to swallow pills, or rely on feeding tube for administration of medications (ie PEG, NG tubes) then solution formulation Palbociclib will be utilized

5.1.2.2.1.2.1 Palbociclib solution should be taken at approximately the same time each day. It does not need to be taken with food.

5.1.2.2.1.2.2 Patient administration directions using syringe are detailed in Pfizer Approved 'Administration Instruction' Handouts (Appendix C- Administration Instructions for Oral Dose Using Syringe and Appendix D- Administration Instructions for Each Dose via NG Tubes)

5.1.2.2.2 Palbociclib solution will be available by late January/ early February 2018 for patients who cannot swallow the Palbociclib capsules.

5.1.2.2.2.1 Patients who begin the study receiving the oral solution will remain on the solution for the duration of their time on treatment in the study.

5.1.2.2.2.2 Patients, who begin the study receiving capsules but develop difficulty swallowing the capsules and did not have disease progression, will be allowed to switch to the Palbociclib oral solution. These patients will then remain on the oral solution for the duration of their time on treatment in the study.

5.1.2.2.3 Patients should be instructed that if they vomit any time after taking a dose of Palbociclib, that they must not "make it up" with an extra dose, but instead resume subsequent doses as prescribed. Missed doses may be taken late, up to 6 hours after the scheduled dose, otherwise should be skipped and reported to the investigators.

5.1.3 Maintenance Single Agent Palbociclib

REGIMEN DESCRIPTION					
Agent	Premedications; Precautions	Dose	Route	Schedule	Cycle Length
Palbociclib	Capsules -Swallow capsules whole. Do not cut, chew, or crush	125 mg daily	Capsule or Solution	Days 1-21	4 weeks (28 days)

	
-Should be taken with food at approximately the same time each day
 
Solution
 
- Should be taken at approximately the same time each day. Does not need to be taken with food
				
--	--	--	--	--	--

5.1.3.1 Single agent palbociclib will be administered in a matter identical to that described in Section 5.1.2.2

5.1.4 Compliance and Monitoring

5.1.4.1 The patients will be asked to bring medication bottles to each follow-up visit, and remaining pills in bottle will be counted at each visit to document compliance. This information will be recorded in each patient's data file.

5.1.4.1.1 If patients are being treated with oral solution, they will be asked to return the bottles in clear Ziplock bag. For drug accountability, research staff may use a best approximation (in units of milliliters) as to the remaining solution as they may be unable to open HDPE bottles

5.1.4.2 Drug Administration will be provided to record compliance with drug administration, route of administration (by mouth or feeding tube) as well as document dose adjustments.

5.2 Toxicities and Dose Modifications

Any patient who receives treatment on this protocol will be evaluable for toxicity. Each patient will be assessed for the development of toxicity according to the Time and Events Table (Section 6.1). Toxicity will be assessed according to the NCI Common Terminology Criteria for Adverse Events (CTCAE), version 4.03. Dose adjustments should be made according to the system showing the greatest degree of toxicity.

5.2.1 Dosing Interruptions

Patients experiencing any of the following adverse events should have their treatment interrupted/delayed

- Uncomplicated Grade 3 neutropenia (ANC<1000/mm³)
- Grade 3 neutropenia (ANC <1000/mm³) associated with a documented infection of fever ≥ 38.5° C
- Grade 4 neutropenia (ANC <500/mm³)
- Grade 4 thrombocytopenia (platelet count < 25,000/mm³)
- Grade ≥ 3 non-hematologic toxicity (including nausea, vomiting, diarrhea, fatigue, and hypertension only if persisting despite optimal medical treatment)

Appropriate follow up assessments should be done until adequate recovery occurs as assessed by the investigator. Criteria required before treatment can resume are described in Section 5.2.2.

Doses of palbociclib \pm carboplatin infusions may be held as needed until toxicity resolution. Depending on when the adverse event resolved, a treatment interruption may lead to the patient missing all subsequent planned doses within that same cycle or even delay the initiation of the subsequent cycle. If the adverse event that led to the treatment interruption recovers within the same cycle, then re-dosing in that cycle is allowed. Doses omitted for toxicity are not replaced within the same cycle. The need for a dose reduction at the time of treatment resumption should be based on the criteria in Section 5.2.3.

In the event of a treatment interruption for reasons other than treatment-related toxicity (ie non-cancer related surgery) lasting >2 weeks, treatment resumption will be decided in consultation with the co-principal investigators.

5.2.2 Dose Delay

Retreatment following treatment interruption for treatment-related toxicity or at the start of a new cycle may not occur until all of the following parameters have been met:

- Platelet count $\geq 50,000/\text{mm}^3$
- ANC $\geq 1000/\text{mm}^3$ and no fever
- Grade 3 or higher treatment-related non-hematologic AEs (including nausea, vomiting, diarrhea, and hypertension only if persisting despite optimal medical treatment), with the exception of alopecia, have recovered to Grade ≤ 1 or baseline (or, at the investigator's discretion, Grade ≤ 2 if not considered a safety risk for the patient)

If a treatment delay results from decline in hematologic parameters, the frequency of blood count assessments should be increased as clinically indicated. G-CSF (Filgrastim or Peg-filgrastim) may be given for neutropenia at the investigator's discretion.

If these parameters are met within 2 weeks of treatment interruption or cycle delay, treatment may be resumed. Please see Section 5.2.3 for dose reductions at the time of treatment resumption.

If these parameters have not been met after 2 weeks of dosing interruption (including the scheduled 1 week off Palbociclib treatment) or 2 weeks of cycle delay, permanent treatment discontinuation should be considered. Treatment resumption for patients recovering from toxicity after > 2 weeks of treatment interruption or cycle delay but deemed to be deriving obvious clinical benefit per the investigator's best medical judgement is left at the investigator's discretion.

A new cycle only starts when the criteria listed above are met and treatment with palbociclib \pm carboplatin may be administered. Otherwise, initiation of the new cycle must be delayed until such criteria are met. In the event that the start of a new cycle is delayed due to treatment related toxicity, procedures required on Day 1 of the given cycle will be performed when palbociclib \pm carboplatin is resumed. New Day 1 procedures that were performed prior to knowing the need to delay the start of the cycle do not need to be repeated 1) if not required to

determine whether study drugs may be resumed and 2) if performed within 7 days prior to study drug resumption.

5.2.3 Dose Reductions

Following dosing interruption or cycle delay, the dose of the study drugs may need to be reduced when treatment is resumed.

No specific dose adjustments are recommended for Grade 1/2 treatment-related toxicity.

Dose reduction of palbociclib and carboplatin by 2 dose levels will be allowed depending on the type and severity of toxicity encountered (Table 3 and 4). Patients requiring more than 2 dose reductions will be discontinued from the study and entered into the follow-up phase.

Once a dose has been reduced for a given patient, all subsequent cycles should be administered at that dose level, unless further dose reduction is required. Dose re-escalation is not allowed.

Table 3: Study Drug Dose Levels

Palbociclib Dose Levels

Dose Level	Dose	Dispensed as
0 (starting dose)	125 mg daily, days 1-14	125 mg capsules OR 5 mL solution
-1	100 mg daily, days 1-14	100 mg capsules OR 4 mL solution
-2	75 mg daily, days 1-14	75 mg capsules OR 3 mL solution

Carboplatin Dose Levels

Dose Level	Dose
0 (starting dose)	AUC= 5, day 1
-1	AUC= 4, day 1
-2	AUC= 3, day 1

Table 4: Dose Modifications for Treatment Related Toxicities Requiring Treatment Interruption/Delay or Persisting Despite Optimal Medical Treatment

Toxicity	Restart Palbociclib Treatment at:	Restart Carboplatin Treatment at:
Uncomplicated Grade 3 neutropenia (ANC <1000/mm ³)	Same dose level	Same dose level
Grade 3 neutropenia (ANC <1000/mm ³) associated with a documented infection or fever ≥ 38.5° C	↓ 1 dose level	↓ 1 dose level

Grade 4 neutropenia ($ANC < 500/mm^3$)	↓ 1 dose level	↓ 1 dose level
Grade 4 thrombocytopenia (platelet count $< 25,000/mm^3$)	↓ 1 dose level	↓ 1 dose level
Grade ≥ 3 non-hematologic toxicity (including nausea, vomiting, diarrhea, and hypertension only if persisting despite optimal medical treatment)	↓ 1 dose level	↓ 1 dose level
Note: G-CSF (Filgrastim or Peg-filgrastim) may be added for low ANC at treating physician's discretion.		

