Exclusion Criteria	
 1. Previous treatment with cytotoxic chemotherapy therapy in the recurrent/metastatic setting. Previous treatment with non-cytotoxic agents and/or concurrent chemoradiation in the recurrent/metastatic setting is permitted. 2. Gastrointestinal abnormalities causing impaired absorption precluding administration of medications by mouth or feeding tube. 3. Evidence of untreated or progressive brain metastases, spinal cord compression, or carcinomatous meningitis. 4. A serious uncontrolled medical disorder or active infection that would impair their ability to receive study treatment. 5. Dementia or significantly altered mental status that would prohibit the understanding or rendering of informed consent and compliance with the requirements of this protocol. 6. Patients (male and female) having procreative potential who are not willing or not able to use 2 adequate methods of contraception or practicing abstinence during the study and for 90 days following their last dose of treatment. 7. Women who are pregnant or breast-feeding. 8. Patients residing in prison. 9. Prior experimental therapy within 30 days of enrollment. 10. Availability of curative treatment option for the patient's cancer, whether surgery, chemotherapy, radiation, or combination thereof, unless the patient has documented refusal of curative treatment. 11. Patients with a history of severe allergic reaction to cisplatin or carboplatin

Study Product(s), Dose, Route, Regimen	
Carboplatin + Palbociclib Cohort Palbociclib (Ibrance), dose= 125 mg daily, days=1-14, cycle length: 21 days Carboplatin (IV), dose= AUC 5, day= 1, cycle length: 21 days
 
Maintenance Palbociclib Palbociclib (Ibrance) 125 mg daily, days 1-21, cycle length: 28 days

Duration of Administration	Study drugs will be administered in an open label fashion until progression, intolerance, or patient preference.
Reference Therapy	A historical control will be utilized
Statistical Methodology	This is an open-label multi-institution single arm Phase II study with a two-stage design

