6.0 STUDY PROCEDURES

6.1 Time and Events Table

6.1.1 Calendar

	Screening ¹	Treatment										Maintenance	Every 8 weeks from Cycle 7, Day 1	End of Treatment	Survival
		Cycle 1			Cycle 2		Cycle 3	Cycle 4	Cycle 5	Cycle 6	Cycle 7				
Day of Cycle		1	8	14	1	14	1	1	1	1	1	1	EOT ⁹	Survival ¹⁰	
Informed Consent	X														
Demographics	X														
Inclusion/Exclusion Criteria	X														
Tumor Biopsy for Correlative Analysis ¹⁴	X														
Interim Biopsy for Correlative Analysis ^{12,16}						X ³									
Tumor Biopsy to confirm progression ^{15,16}													X		
H&P, Relevant Medical History	X														
Pregnancy Test	X	X													
Clinic Visit ⁴	X	X		X ^{2,13}		X ^{2,13}	X								
Performance Status	X	X		X ^{2,13}		X ^{2,13}									
Physical Exam ⁴	X	X		X ^{2,13}		X ^{2,13}									
QOL Survey ⁴		X		X ^{2,13}		X ^{2,13}									
Adverse Effects Assessment ⁵		X		X ^{2,13}		X ^{2,13}	X								

	Screening ¹	Treatment										Maintenance		Every 8 weeks from Cycle 7, Day 1	End of Treatment	Survival
		Cycle 1			Cycle 2		Cycle 3	Cycle 4	Cycle 5	Cycle 6	Cycle 7	Cycle 8+				
Day of Cycle		1	8	14	1	14	1	1	1	1	1	1	EOT ⁹	Survival		
CBC ⁶	X	X		X ²	X ^{2,13}	X ²	X ^{2,13}		X							
CMP ⁶	X	X			X ^{2,13}		X ^{2,13}		X							
Correlative: Salivary Rinse ⁷		X	X ²		X ^{2,13}		X ^{2,13}									
Correlative: 2 Serum Tubes ⁷		X	X ²		X ^{2,13}		X ^{2,13}									
Correlative: 1 Serum Tube ⁷		x														
CT Imaging ⁸	X						X ³		X ³		X ³		X ³			
Palbociclib Dosing ¹¹		125 mg daily, days 1-14. Cycle Length: 21 Days										125 mg daily, days 1-21. Cycle Length: 28 Days				
Carboplatin Infusion		X			X		X	X	X	X						
Survival Assessment														X ¹⁰		

1= May be performed within 28 days of Cycle 1, Day 1 unless otherwise specified

2= May be performed +/- 4 days

3= May be performed +/- 7 days

4= Vital signs, physical exam, ECOG performance status will be checked at each visit as well administration of FACT H&N questionnaire (see Appendices B and C)

5= Toxicities will be evaluated using CTCAE version 4.03

6= Labs will be obtained pre-dose. CMP includes Basic Metabolic Profile (Na, K, Cl, CO2, BUN, Cr, Glu), AST/SGOT, ALT/SGPT, Alk Phos, T Bili, Albumin, Ca, and Total Protein

7= Collection tubes (see lab manual) will be drawn and sent to the [name] lab for DNA isolation and long term storage. May be performed +/- 4 days

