8= CT Neck and Chest will be obtained in all patients. Further imaging (ie CT Abdomen/Pelvis, Bone Scan) will be performed as deemed appropriate by the treating physician. Initial staging imaging may be performed within 28 days prior to treatment

9= Will be performed within 30 days after discontinuation of study treatment. If the patient refuses to present for a clinic visit, phone contact will be made within 30 days after discontinuation of study treatment

10= Survival assessment can be done by phone and will be performed once every three months (+/- 1 month)

11= Will be administered orally on a daily basis, dose as defined per protocol

12=Biopsy at Cycle 2 will be offered if clinically safe and feasible. Patients may refuse repeat biopsy

13= In the event that the start of a new cycle is delayed due to treatment related toxicity, procedures required on Day 1 of the given cycle will be performed when palbociclib ± carboplatin is resumed. New Day 1 procedures that were performed prior to knowing the need to delay the start of the cycle do not need to be repeated 1) if not required to determine whether study drugs may be resumed and 2) if performed within 7 days prior to study drug resumption.

14= A biopsy demonstrating metastatic disease must be obtained within the 56 days prior to study treatment. FFPE core biopsy is preferred, however, if not clinically feasible or safe to obtain a core biopsy a block made from several FNA passes is acceptable. No systemic therapy (i.e. immunotherapy) may have been administered since obtaining the biopsy, if so, a new biopsy is needed.

15= If treating physician deems biopsy to be either unsafe or not clinically feasible, this must be documented and patient may forego repeat biopsy

16= FFPE core biopsy is preferred. However, if not clinically feasible or safe to obtain a core biopsy, contact coordinating site PIs ([name]) as a block made from several FNA passes is acceptable after PI approval.

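### The maintenance dose is stated without reference to earlier reductions, while Section 5.2.3 bars re-escalation, and no dose level is defined for the 21-of-28-day schedule

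*Combined protocol and SAP*

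**What the plan says.** Section 5.1.1 sets the move to maintenance. The entry condition is "After 6 cycles of Carboplatin + Palbociclib, if patients continue to garner a response to therapy", and for those patients "they will be transitioned to maintenance single agent palbociclib at a dose of 125 mg daily, days 1-21, cycle length: 28 days". The synopsis gives the same regimen ("Palbociclib (Ibrance) 125 mg daily, days 1-21, cycle length: 28 days"), as do the regimen table in Section 5.1.3 and the palbociclib row of the calendar in Section 6.1.1 ("125 mg daily, days 1-21. Cycle Length: 28 Days"). None of these places mentions a patient who is already on a lower dose.

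Section 5.2.3 governs reductions: "Once a dose has been reduced for a given patient, all subsequent cycles should be administered at that dose level", unless a further reduction is needed, and "Dose re-escalation is not allowed". Table 3 in that section lists palbociclib levels 0, -1 and -2 at 125, 100 and 75 mg, each tied to days 1-14; the lowest reads "75 mg daily, days 1-14". Table 4 then tells sites to restart one level lower after most toxicities that interrupt treatment.

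Two pieces of text might have linked these rules. Section 5.1.3.1 points back to Section 5.1.2.2, which covers how the drug is taken. Calendar footnote 11 says "Will be administered orally on a daily basis, dose as defined per protocol".

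**The concern.** A patient who reaches cycle 7 at 100 mg or 75 mg meets two instructions that nothing reconciles. One states 125 mg for maintenance; the other keeps the reduced level and forbids going back up. Under Table 4 such a patient was reduced for grade 3 neutropenia with infection or fever, grade 4 neutropenia, grade 4 thrombocytopenia, or non-hematologic toxicity of grade 3 or worse. An unintended return to the starting dose would fall on patients with documented intolerance.

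The trial may run at up to three sites, which could resolve the point differently. Maintenance exposure would then differ by site for reasons unrelated to the patient, and maintenance adverse events, part of a secondary objective, would be pooled over unlike dosing.

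The gap in Table 3 is separate and also reaches patients who were never reduced. If a Table 4 trigger first occurs in maintenance, the patient is sent one level down to a level written for a different schedule.

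**Working it through.** The plan states no figure on this point, so there is none to reproduce. The check is a comparison of texts plus simple dose arithmetic.

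**Inputs.** Combination schedule: 14 dosing days in 21 (Section 5.1.2). Maintenance schedule: 21 dosing days in 28 (Section 5.1.3). Levels: 125, 100 and 75 mg (Table 3). Maintenance dose as written: 125 mg.

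**Step 1: the texts side by side.**

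| Place | Palbociclib in maintenance | Exception for earlier reduction |
|---|---|---|
| Synopsis | 125 mg, 21 of 28 days | none stated |
| 5.1.1 | 125 mg, 21 of 28 days | none stated |
| 5.1.3 table | 125 mg, 21 of 28 days | none stated |
| 6.1.1 calendar | 125 mg, 21 of 28 days | none stated; footnote 11 refers back to the protocol |
| 5.2.3 | not named; a reduced level holds for all later cycles | re-escalation barred |
| Table 3 | not named; levels written for days 1-14 only | not addressed |

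No text says which of these governs a reduced patient at cycle 7.

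**Step 2: change per dosing day if the maintenance text is applied literally.** Formula: 125 / current dose − 1.

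- From level 0: 125/125 − 1 = 0%
- From level -1: 125/100 − 1 = +25%
- From level -2: 125/75 − 1 = +67%

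**Step 3: average daily dose, separating the conflict from the planned change of schedule.** Formula: mg × dosing days / cycle length.

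| Level | Combination (14/21) | Same mg on 21/28 | 125 mg on 21/28 |
|---|---|---|---|
| 0 (125 mg) | 83.3 | 93.75 | 93.75 |
| -1 (100 mg) | 66.7 | 75.0 | 93.75 |
| -2 (75 mg) | 50.0 | 56.25 | 93.75 |

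The schedule change alone adds 93.75/83.3 − 1 = 12.5%, and it does so at every level, including for patients never reduced. What the conflict adds is the step from the third column to the fourth: 93.75/75 − 1 = +25% and 93.75/56.25 − 1 = +67%, the same as in Step 2. The full change from combination to maintenance is the product of the two: 1.125 × 1.25 = 1.41 and 1.125 × 1.667 = 1.88.

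**Step 4: does Section 5.2.3 settle the matter if it prevails?** Only the milligrams. Levels -1 and -2 are defined as 100 mg and 75 mg on days 1-14. Kept literally, 14 dosing days do not correspond to a 28-day cycle with 21. A site would have to decide the days itself, and would face the same question for a reduction that first arises in maintenance.

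**Step 5: timing against the primary endpoint.** Six cycles of 21 days are 126 days, or 18 weeks. Disease control is assessed at 12 weeks, so without delays maintenance begins about six weeks later.

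**The case against.** The strongest reply is that 125 mg is a nominal dose everywhere. The synopsis, Section 5.1.1, the Section 5.1.2 table and the calendar also print 125 mg for the combination cycles without an exception, and nobody would take that to cancel a reduction in cycles 2 to 6. Section 5.2.3 is the only text addressed to reduced patients, and its rule for later cycles has no phase limit. The calendar numbers maintenance as cycles 7 and 8+. Sections 5.2.1 and 5.2.2 speak of palbociclib with or without carboplatin, which fits single-agent cycles. Footnote 11 defers to the protocol, and Section 9.2 ties the solution volume to the dose the investigator prescribes.

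Much of this stands. A reader might infer that no reduced patient could satisfy both rules, or that the protocol orders re-escalation. The documents do not support that, because the nominal-dose reading is reasonable and would keep the reduced milligrams. But it remains an inference: none of the texts just cited names maintenance dosing or states an order of precedence. It also leaves Step 4 unanswered.

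A reader might also take the rises of 41% and 88% in average daily dose (Step 3) as the size of the conflict. They include the planned schedule change, which applies to unreduced patients too; the part due to the conflict is 25% and 67%.

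**Conclusion.** The point holds as a gap in the dosing rules: precedence at the switch is unstated, and no dose levels exist for the 21-of-28-day schedule. The first matters only if a site applies the maintenance text literally, in which case the dose per dosing day rises by 25% or 67%. The second is present on any reading.

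The number of patients affected cannot be derived. The documents do not give the share who reach cycle 7 or the share reduced by then. The grade 4 neutropenia rates in the background (6% to 10.4%) come from breast cancer trials with endocrine therapy and should not be carried over to patients still responding after six cycles of this doublet.

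A reader might infer that the main result is compromised. It is not: the 12-week endpoint precedes maintenance, and the two-stage rule does not depend on it. Progression-free and overall survival are described by Kaplan-Meier estimates with no planned comparison, and the documents do not show that these would be distorted. What is at stake is patient safety and the clarity of maintenance exposure and adverse-event data. Severity: should fix.

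**What to change.** Reconcile the synopsis, Sections 5.1.1 and 5.1.3 and the calendar with Section 5.2.3, so that one stated rule governs previously reduced patients when they move to maintenance, and cross-refer to it from each place that prints the maintenance dose. Make Table 3 state how its levels apply to the 21-of-28-day schedule, both for reductions carried over and for those that Table 4 triggers during maintenance. Which rule and which levels apply is a clinical decision for the sponsor; this review takes no view on it.

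The cost is a short protocol clarification sent to all sites. Sample size, decision rules and planned analyses do not change.

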8.1.1 Contraindications

8.1.1.1 Carboplatin is contraindicated in patients with a history of severe allergic reactions to cisplatin or other platinum containing compounds

8.1.1.2 Carboplatin should not be employed in patients with severe bone marrow depression or significant bleeding

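### Table 4's general row for Grade ≥3 non-hematologic toxicity lists a reduced carboplatin restart with no exception for severe carboplatin allergy, which Section 8.1.1.1 makes a contraindication

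*Combined protocol and SAP*

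**What the plan says.** Three places govern what happens after a serious non-hematologic event.

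- **Section 5.2.1** interrupts treatment for any Grade ≥3 non-hematologic toxicity. On restarting within a cycle it says: "If the adverse event that led to the treatment interruption recovers within the same cycle, then re-dosing in that cycle is allowed". It adds: "Doses omitted for toxicity are not replaced within the same cycle".
- **Section 5.2.2** sets the recovery condition. Grade 3 or higher treatment-related non-hematologic events must, "with the exception of alopecia, have recovered to Grade ≤ 1 or baseline", or to Grade ≤2 at the investigator's discretion. It continues: "If these parameters are met within 2 weeks of treatment interruption or cycle delay, treatment may be resumed".
- **Section 5.2.3, Table 4** gives the restart dose. The row for "Grade ≥ 3 non-hematologic toxicity" lowers both drugs by one level. Table 3 shows that carboplatin then goes from AUC 5 to AUC 4 for a patient at the starting dose.

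Allergy is dealt with elsewhere. Section 8.1.1.1 states: "Carboplatin is contraindicated in patients with a history of severe allergic reactions to cisplatin or other platinum containing compounds". Exclusion 3.2.11 bars patients with a history of severe allergic reaction to cisplatin or carboplatin. Section 8.1.2.5 warns of reactions within minutes of administration, calls for supportive therapy, and notes a higher risk, including anaphylaxis, after earlier platinum. Section 8.1.4.2 gives a hypersensitivity rate of 2% and says reported reactions were managed successfully.

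**The concern.** A patient who has a severe allergic reaction to carboplatin on study now has the history that 8.1.1.1 describes. The dosing rules treat that patient like anyone else with a Grade ≥3 non-hematologic event: wait for recovery, then restart carboplatin at the next level down. A lower dose is a sensible response to dose-related toxicity. It does not answer a contraindication, which applies at any dose.

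At stake is re-exposure to carboplatin in a patient at risk of anaphylaxis. Sites are likely to consult the dosing table when deciding on the next cycle, and it does not send them to 8.1.1. The question can arise repeatedly, because Section 5.1.1 plans six carboplatin cycles and every patient has had platinum by Cycle 2.

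**Working it through.** There is no plan figure to reproduce on this point, so the main check is textual. I followed one patient through the rules.

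1. *Event.* A Grade 3 allergic reaction to carboplatin occurs on Day 1 of a cycle. It is non-hematologic, so 5.2.1 interrupts treatment. The qualifier about persistence despite optimal treatment covers named events such as nausea and hypertension. Allergy is not among them.
2. *Recovery.* The reaction resolves with supportive care, as 8.1.4.2 says reported reactions did. The Grade ≤1 condition in 5.2.2 is met. The only exception there is alopecia, and it loosens the rule, since alopecia need not recover. Nothing in 5.2.2 bars retreatment after a particular kind of event.
3. *Timing.* Carboplatin is given on Day 1 only, and omitted doses are not replaced within the cycle. For carboplatin the restart question therefore arises mainly at the next cycle.
4. *Dose.* Table 4 lists one level lower: AUC 4, which is 4/5 = 80% of the starting dose.
5. *Contraindication.* Section 8.1.1.1 covers cisplatin and other platinum compounds. Carboplatin falls under that class wording and is named outright in 3.2.11. The patient now has the history described.

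Steps 4 and 5 give incompatible answers if the table is taken literally, and neither section refers to the other. Sections 8.1.2.5 and 8.1.4.2 do not settle the matter: they describe management of a reaction and contain no rule on stopping or rechallenge.

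**How often it could arise.** Inputs: 40 patients (5.1.1) and a 2% hypersensitivity rate that is not split by grade (8.1.4.2).

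- Expected reactions of any grade: 40 × 0.02 = 0.8.
- Chance of at least one: 1 − (1 − 0.02)^40 = 0.55.

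The documents give no severe-only rate. The rates below are assumptions, shown only for range:

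| Assumed rate of severe reactions | Expected in 40 | Chance of at least one |
|---|---|---|
| 0.5% (a quarter of the 2%) | 0.2 | 18% |
| 1% (half of the 2%) | 0.4 | 33% |
| 2% (all of the 2%) | 0.8 | 55% |
| 5% (above the 2%, to allow for earlier platinum) | 2.0 | 87% |

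These count severe reactions, not unsafe doses. The number of patients given carboplatin again lies between zero, if every site follows 8.1.1.1, and the number of severe reactions. The documents offer nothing that would narrow that range.

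**The case against.** The strongest reply is that the texts can be reconciled. Table 4 answers at what dose a drug restarts; 8.1.1.1 answers the prior question of whether it may be given at all. Restart is permissive throughout: the recovery criteria are minimum conditions, after which treatment may resume. Section 5.4 ends treatment for an unacceptable adverse event, 5.6 requires removal from protocol therapy when a 5.4 criterion applies, and 5.8.5 lets the physician stop. Sections 8.1 and 9.1 also send sites to labelling that is not part of these documents, so nothing can be said about what it tells them.

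Most of this stands. A reader might infer that the protocol requires rechallenge, and it does not. A site that applies 8.1.1.1 avoids the unsafe dose. What the reply does not remove is that the operative rule lists a specific carboplatin dose for a patient in whom carboplatin is contraindicated. The routes in 5.4 and 5.8.5 rest on judgement, and neither names allergy.

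A reader might also infer that lowering palbociclib for a carboplatin reaction is an error, especially as "Dose re-escalation is not allowed" and only two reductions are permitted. The documents do not support that. Every row of Table 4 that reduces a dose reduces both drugs, whichever caused the event. That is the table's general design and conflicts with nothing in 8.1.1.1. Sections 5.2.1 and 5.2.2 refer to palbociclib with or without carboplatin, so palbociclib alone may be contemplated, but no rule links it to allergy.

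**Conclusion.** Wrong as written, but minor. Table 4, read with 5.2.1 and 5.2.2, omits an exception that 8.1.1.1 makes necessary. The protocol does not mandate rechallenge, and a careful site has several grounds for stopping.

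The event is infrequent: about 0.8 reactions of any grade in 40 patients, if the 2% in 8.1.4.2 applies to this population. The severe share and the share of those re-dosed are unknown, so the number of contraindicated doses cannot be estimated and may be zero. Nothing here changes the type I error, power or analysis in Section 11. The reason to act is that the possible consequence for an individual patient is serious and the correction is simple.

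**What to change.** Add a footnote to the Grade ≥3 non-hematologic row of Table 4, with a cross-reference in 5.2.2, along these lines:

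*This row does not apply to a severe allergic reaction or anaphylaxis attributed to carboplatin; carboplatin is permanently discontinued (see 8.1.1.1).*

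The sponsor should state which CTCAE grade counts as severe, because 8.1.1.1 does not tie the word to a grade. Grade ≥3 would be consistent with the row's own threshold. Whether palbociclib then continues alone, and at what dose, is a clinical choice for the sponsor. It would be useful to state it in the same amendment, but it is not part of the error.

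The cost is one footnote and one cross-reference in a protocol amendment, with no added patients, visits or procedures and no change to the statistical design.
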